### **9.9.6 Randomization**

Patients who meet all of the inclusion criteria and none of the exclusion criteria will be randomized in a [REDACTED]

[REDACTED]  
[REDACTED]  
[REDACTED]

## 10 STATISTICAL CONSIDERATIONS

### 10.1 Sample Size Determination

The required sample size is 82 participants based on the below specifications that have received at least 1 dose of posoleucel or PBO.

The sample size was determined based on the following specifications:

1. Superiority study comparing posoleucel plus SoC to placebo plus SoC
2. Primary endpoint is success or failure based on clearance of ADV viremia at Day 29 of the Primary Study Period
3. Allocation (posoleucel:placebo) is █
4. Chi-square test
5. Two-sided alpha = 0.05
6. True success rate (defined as clearance of virus) for posoleucel = 0.55
7. True success rate (defined as clearance of virus) for placebo = 0.25
8. Power = 80%

A SSRE and futility analysis will be performed after approximately 40 participants have completed Day 29 of the Primary Study Period. Details of the SSRE and futility analysis will be provided in the SSRE Plan prior to conducting the interim analyses.

### 10.2 Populations for Analyses

For purposes of analysis, the following populations are defined:

Population	Description
Intent-to-Treat (ITT)	All randomized participants. Participants will be analyzed according to the randomized study treatment.
Modified ITT	All randomized participants who receive at least one dose of posoleucel or placebo. All efficacy endpoints will be analyzed based on the mITT Population and these analyses will be considered the primary analyses of efficacy. Participants will be analyzed according to the randomized study treatment.
Per Protocol (PP)	All ITT participants who receive any amount of posoleucel or placebo and who do not have any major protocol deviations deemed potentially to impact efficacy or its evaluation, as defined in the SAP. All efficacy endpoints will also be analyzed based on the PP Population, and these analyses will be considered secondary analyses of efficacy. Participants will be analyzed according to the randomized study treatment.
Safety	All participants who receive any amount of posoleucel or placebo and have at least 1 post-treatment safety assessment. All safety analyses will be based on the Safety Population. Participants will be analyzed according to the actual study treatment received.

## 10.3 Statistical Analyses

The SAP will be developed and finalized before database lock and will describe in detail the planned statistical analyses and the procedures for handling missing data. This section is a summary of the planned statistical analyses. A separate SSRE Plan will be developed and finalized before conducting the interim analysis.

Summary statistics will be presented by treatment group for the Primary Study Period and by cross-over group (Posoleucel/Placebo or Placebo/Posoleucel) based on the treatments received for the Cross-Over Period. Unless otherwise stated, continuous variables will be summarized using the number of non-missing observations, mean, standard deviation, median, minimum, and maximum values as descriptive statistics. Categorical variables will be summarized using the frequency count and the percentage of participants in each category as descriptive statistics.

### 10.3.1 Efficacy Analyses

All efficacy endpoints will be analyzed and formally compared between randomized treatment groups using statistical tests based on data from the Primary Study Period. In addition, for purposes of complete reporting, results for these endpoints will be reported, if appropriate, for data from the Cross-Over Period by treatment received in the Cross-Over Period, but no formal comparisons or statistical tests will be made.

The primary and key secondary efficacy endpoints will be analyzed under the estimand framework. The estimand attributes will be described in detail in the SAP.

In order to control the overall type 1 error rate, a sequential approach will be used to analyze the primary and key secondary efficacy endpoints, with undetectable viremia (less than LLOQ) at Day 29 of the Primary Study Period as the primary efficacy endpoint, followed by progression from viremia to target organ disease (for participants without target organ disease at screening), progression of target organ disease (for participants with target organ disease at screening), or non-relapse mortality during the study as the key secondary efficacy endpoint.

For AdV viral endpoints at Day 29 or Week 4 visit, a 14-day window will be applied to the Day 29 visit. The last observed plasma AdV DNA result through Day 29 + 14 days (up to 43 days post first infusion) will be used for the analysis. Participants who cross over on or before Day 29 will be treated as failure.

All efficacy endpoints will be analyzed based on the mITT Population, and these analyses will be considered the primary analyses of efficacy. The primary and key secondary efficacy endpoints will also be analyzed based on the ITT and PP Population to assess the robustness of the primary analysis results.

#### 10.3.1.1 Primary Efficacy Endpoint Analysis

The primary efficacy endpoint, undetectable viremia (less than LLOQ) at Day 29 of the Primary Study Period, will be summarized by treatment group using the count and percentage, together with an exact (Clopper-Pearson) 95% confidence interval for the true percentage.

The null hypothesis is that the true percentage for posoleucel plus SoC is less than or equal to the true percentage for placebo plus SoC, and the alternative hypothesis is that it is greater. This endpoint will be analyzed using logistic regression. The model will include a term for treatment and the following covariates: level of viremia at Baseline ( $\geq 10,000$  copies/mL or  $< 10,000$

copies/mL AdV DNA), age ( $\geq 12$  years or  $< 12$  years) and absolute lymphocyte count at Baseline. The null hypothesis will be tested using a one-sided test of the effect of treatment at the 0.025 significance level. Missing data imputation will be described in the SAP.

#### 10.3.1.2 Key Secondary Efficacy Endpoint Analysis

The key secondary efficacy endpoint will be tested sequentially after the primary endpoint reaches statistical significance. The key secondary efficacy endpoint, progression from viremia to target organ disease (for participants without target organ disease at screening), progression of target organ disease (for participants with target organ disease at screening), or non-relapse mortality during the study, will be analyzed in the same manner as the primary efficacy endpoint.

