## STUDY DESIGN AND DURATION:

This is a Phase 3, multicenter, randomized, double-blind, placebo-controlled study to assess the safety and efficacy of posoleucel as compared to placebo for the treatment of AdV infection in pediatric and adult recipients of HCT with AdV infections receiving SoC.

Approximately 82 eligible patients may be randomized [ ] to receive [ ] sequential infusions of posoleucel or placebo (separated by [ ]). Randomization will be stratified [ ]

---

[REDACTED]  
[REDACTED]

The presence or absence of adenovirus target organ disease at screening will be determined initially by the Investigator (using the criteria in [Appendix 8](#)) and reviewed subsequently by the Adjudication Committee for analysis purposes.

The Primary Study Period is 4 weeks (28 days) for evaluation of efficacy, including the primary endpoint, plus 20 weeks for safety follow-up, for a total study duration of 24 weeks. For participants who cross-over, the Cross-Over Period is 4 weeks (28 days), plus 20 weeks for safety follow-up. Participants who experience recurrence and receive an additional dose will have safety follow-up for 20 weeks after the final dose.

At Day 29, all participants will be assessed for the primary endpoint, virologic response.

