#### 10.3.1.3 Other Secondary Efficacy Endpoint Analyses

Following the key secondary analysis, progression from viremia to target organ disease and progression of target organ disease will be analyzed as separate subgroups in a step-down manner. If any participants cross over prior to Day 29, they will be considered as having had progression, because the necessary condition for cross-over is that the participant progressed to active target organ disease (for participants without target organ disease at screening) or experienced progression of target organ disease (for participants with target organ disease at screening).

The AAUC for plasma AdV viremia ( $\log_{10}$  copies/mL AdV DNA), as assayed by qPCR, through Day 29 of the Primary Study Period will be summarized by treatment group using descriptive statistics (number of non-missing observations, mean, median, standard deviation, minimum, and maximum). The null hypothesis for this endpoint is that the true mean for posoleucel is greater than or equal to the true mean for placebo, and the alternative hypothesis is that it is less. The null hypothesis will be tested using a one-sided, two-sample t-test with a 0.025 significance level.

The following secondary efficacy endpoints will each be analyzed in the same manner as the primary efficacy endpoint: achieving AdV viremia  $< 400$  copies/mL AdV DNA at Day 29 of the Primary Study Period and AdV disease recurrence during the study among participants who had clearance of AdV viremia (prior to any cross-over).

The Kaplan-Meier estimated median time to resolution of AdV viremia will be presented for each treatment group, together with the 95% confidence interval for the true median. The number and percentage of censored and uncensored participants will be presented by treatment group. The null hypothesis for this endpoint is that the true distributions of time to resolution of AdV viremia are equal for posoleucel and placebo, and the alternative hypothesis is that the true distributions are different, with the time to resolution of AdV viremia being less for posoleucel. The null hypothesis will be tested using a one-sided log-rank test with a 0.025 significance level.

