3.4.1 Primary Efficacy Endpoint Analysis

3.4.2 Primary Analysis of Primary Efficacy Endpoint

The primary efficacy endpoint, undetectable viremia (less than LLOQ) at Day 29 of the Primary Study Period, will be summarized by treatment group using the count and percentage, together with an exact (Clopper-Pearson) 95% confidence interval for the true percentage. The difference in percentages between the two treatments (posoleucel – placebo), together with a 95% exact confidence interval for the true difference, will be presented.

This endpoint will be analyzed using logistic regression. The model will include a term for treatment and the following covariates: level of viremia at Baseline ($\geq 10,000$ copies/mL or $< 10,000$ copies/mL AdV DNA), age (≥ 12 years or < 12 years) and absolute lymphocyte count at Baseline. For participants who discontinued treatment but remain on the study, data collected after treatment discontinuation will be included in the analysis. If a participant doesn't have plasma AdV DNA result in the Day 29 through Day 43 window but has undetectable viremia before Day 29 and after Day 43, it will be imputed as success for the primary endpoint. The deaths related to adenovirus infection on or before Day 29 will be imputed as failure.

Subgroup analyses of the primary endpoint will be performed for both of the randomization stratification variables: (1) level of viremia: $\geq 10,000$ copies/mL and $< 10,000$ copies/mL AdV DNA and (2) age: ≥ 12 years or < 12 years.

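### The key secondary model omits target organ disease at screening, the baseline status that decides which progression event counts; adding it costs little and protects against chance imbalance

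*Protocol*

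**What the plan says.** Protocol 10.3.1.2 defines the key secondary event by status at screening. Participants without target organ disease have an event if they progress from viremia to organ disease. Participants with it have an event if that disease progresses. Non-relapse mortality counts in both groups. The section then says that the endpoint "will be analyzed in the same manner as the primary efficacy endpoint".

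Protocol 10.3.1.1 gives the model so imported: "The model will include a term for treatment and the following covariates: level of viremia at Baseline" (at or above versus below 10,000 copies/mL), age (at or above versus below 12 years) "and absolute lymphocyte count at Baseline". The test is one-sided at 0.025.

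The stratification text is redacted in the protocol, but SAP 3.4.2 reads "Subgroup analyses of the primary endpoint will be performed for both of the randomization stratification variables" and lists two: viremia level and age.

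The Synopsis (Study Design and Duration) says that the Investigator determines target organ disease at screening and that this is "reviewed subsequently by the Adjudication Committee for analysis purposes".

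Protocol 10.3.1.3 adds one further step once the key secondary test is done: "progression from viremia to target organ disease and progression of target organ disease will be analyzed as separate subgroups in a step-down manner".

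SAP Section 1 limits the efficacy analysis to the primary endpoint after termination for futility, and SAP 3.1 plans no hypothesis tests.

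**The concern.** The covariates were chosen for a virologic endpoint, clearance at Day 29, and carried over unchanged to a clinical composite. For that composite, organ disease at screening is an obvious candidate as a prognostic factor, since it changes what counts as an event. The sponsor has already accepted this kind of argument: the Amendment 4 rationale adds lymphocyte count because published data suggest that it predicts clinical outcome strongly. Protocol 3.2 cites mortality of up to 50% once infection progresses to disease, and death is a component of the endpoint.

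Two things are at stake if the status is prognostic. First, the model gives up some power. Second, neither stratification nor the model deals with a chance difference between arms in the share of participants who enter with organ disease. In a trial of 82, that difference could noticeably move the result of the only clinical efficacy endpoint in the alpha-controlled sequence.

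**Working it through.** **1. The plan's own figure.** Inputs from Protocol 10.1: success rates 0.55 and 0.25, chi-square test, two-sided 0.05, 80% power; 1:1 allocation from the Synopsis. The mean rate is 0.40.

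n per arm = [1.96·√(2·0.40·0.60) + 0.8416·√(0.55·0.45 + 0.25·0.75)]² / 0.30² = (1.358 + 0.555)² / 0.09 = 40.7, so 41 per arm and 82 in total. Power at 41 per arm is 80.3%. The 82 reproduces for the primary endpoint. No power is stated for the key secondary endpoint.

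**2. Inputs that the documents do not give (assumed).** Prevalence of organ disease at screening 20% to 40%; various event rates by status. The strength of the status is expressed as its odds ratio (OR) for the event. For example, control rates of 25% without and 60% with disease give (0.60/0.40)/(0.25/0.75) = 4.5.

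**3. Chance imbalance.** The number of diseased participants falling in one arm of 41 is hypergeometric. The totals 16, 25 and 33 of 82 correspond to 20%, 30% and 40%.

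| Prevalence | Imbalance ≥10 points | ≥15 points | ≥20 points |
|---|---|---|---|
| 20% | 16% | 5% | 1% |
| 30% | 34% | 15% | 5% |
| 40% | 37% | 18% | 7% |

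These are probabilities in either direction; half of each works against posoleucel. Imbalance moves in steps of 2/41 = 4.9 points. With 16 diseased, the possible values either side of 15 are 14.6 and 19.5, so the 16% in the first column is also the chance of 14.6 points or more.

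At control rates of 25% and 60%, a 15-point excess shifts the crude difference by 0.15 × (0.60 − 0.25) = 5.25 points.

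**4. Average power, with and without the term.** Simulated logistic Wald test, one-sided 0.025, 41 per arm. Set A uses a conditional treatment OR of 0.25 and three non-prognostic covariates standing in for the planned ones (4,000 or 5,000 trials per run; ranges cover repeat runs).

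| Prevalence; control rates without/with disease | Status OR | Without | With | Gain (points) |
|---|---|---|---|---|
| 20%; 30%/60% | 3.5 | 67% | 68–69% | 1–2 |
| 30%; 25%/60% | 4.5 | 63% | 67% | 4 |
| 40%; 20%/70% | 9.3 | 57–59% | 66–68% | 9–10 |
| 30%; 25%/80% | 12 | 53–55% | 63–64% | 9–11 |

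A further case at 25%/40% (status OR 2) gave 59% and 59%; a repeat gained about 1 point.

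Set B fixes the overall event rates instead (prevalence 20% and 40%, 5,000 trials each).

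| Status OR | 0.50 vs 0.20: without → with | 0.40 vs 0.20: without → with |
|---|---|---|
| 1 | 82% → 82% | 51% → 51% |
| 2 | 82% → 83% | 49–50% → 49–51% |
| 4 | 82% → 85% | 50–51% → 53–55% |
| 8 | 82% → 86–88% | 49–50% → 56–57% |

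**5. Power when chance goes against posoleucel.** Set B at 0.50 vs 0.20, restricted to trials in which posoleucel has at least 6 more diseased participants (6/41 = 14.6 points). This happened in about 6% to 7% of trials at 20% prevalence and 10% to 12% at 40%.

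| Status OR | Without | With |
|---|---|---|
| 2 | 71–77% | 78–83% |
| 4 | 61–67% | 82–83% |
| 8 | 56–57% | 83–85% |

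These rest on about 300 to 570 trials each. With 324 trials and 61% power, the standard error is √(0.61·0.39/324) = 2.7 points.

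**6. Type I error.** At equal rates of 0.40, Set B gives 0.024–0.028 without the term and 0.023–0.027 with it. Other runs spanned 0.020–0.029. The simulation standard error at 5,000 trials is √(0.025·0.975/5000) = 0.002. The overall error is about 0.025 either way. Given an excess of disease on posoleucel at status OR 4, the error without the term falls to 0.000–0.006. Since the overall rate stays near 0.025, the opposite imbalance must push it above 0.025.

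**7. Price in parameters.** At 30% prevalence with 25%/60%, the control rate is 0.7·0.25 + 0.3·0.60 = 0.355. An OR of 0.25 turns 25% and 60% into 7.7% and 27.3%, so the treated rate is 0.7·0.077 + 0.3·0.273 = 0.136. Expected events are 41 × (0.355 + 0.136) ≈ 20. That is 20/4 = 5 per non-intercept term now and 20/5 = 4 with the extra one.

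**The case against.** The strongest reply is that this is an efficiency preference and not an error. Much of it stands:

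- The documents do not show that the status is strongly prognostic. The 50% mortality figure concerns progression to disease, not onset versus worsening by status at screening. At a status OR of 2 the average gain is close to nil.
- A reader might infer that nothing balances organ disease between the arms. Randomization balances it in expectation. What is missing is protection against chance imbalance in this one trial, and baseline viremia and lymphocyte count may absorb part of that.
- A reader might infer that the planned test is invalid. It is not: overall type I error holds with or without the term.
- A reader might call the odds ratio without the term biased. It is closer to 1 because odds ratios are not collapsible. In the example of step 7, (0.136/0.864)/(0.355/0.645) ≈ 0.29 against 0.25 within status groups. That is a different target, not a wrong estimate of the same one.
- Results by status would be visible from the step-down subgroups. This is true, but those analyses follow the key secondary test and do not adjust it.
- A fifth non-intercept term with some 20 events is a real, though small, cost.

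None of this gives a reason to leave the status out. It limits how much may be claimed.

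**Conclusion.** The point holds as a modest improvement to Protocol 10.3.1.2. Three facts are firm: the term is absent, the status decides which progression event counts, and it is not a stratification factor. The benefit depends on assumed prevalences of 20% to 40% and assumed event rates. The average power gain is about 0 to 1 point at a status OR near 2, 1 to 4 points at 3.5 to 4.5, and 5 to 11 points at 8 to 12. The better argument is the unlucky draw: an imbalance of more than 15 points in either direction arises in about 5% to 18% of trials, and an adverse one can cost 15 points of power or more at a status OR of 4. This concerns precision and conditional bias.

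A reader might also infer that the reported results would change. The documents do not support that, because the final SAP drops this endpoint and all hypothesis tests. The point applies to the protocol's prespecified test and to any later analysis of the endpoint.

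**What to change.** In Protocol 10.3.1.2, replace the bare reference to the primary model with a statement that the model also includes target organ disease at screening (yes/no), as reviewed by the Adjudication Committee. Use the same model for the by-Day-29 version of the composite, whose model 10.3.1.3 does not spell out. The abbreviated SAP needs no change; any later plan that takes up this endpoint should carry the term.

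The status is already determined at screening and reviewed for analysis, so no new data are needed. The cost is one more parameter with a limited number of events. The blinded pooled event count should be checked against five non-intercept terms before the model is finalised.

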#### 10.3.1.3 Other Secondary Efficacy Endpoint Analyses

Following the key secondary analysis, progression from viremia to target organ disease and progression of target organ disease will be analyzed as separate subgroups in a step-down manner. If any participants cross over prior to Day 29, they will be considered as having had progression, because the necessary condition for cross-over is that the participant progressed to active target organ disease (for participants without target organ disease at screening) or experienced progression of target organ disease (for participants with target organ disease at screening).

The AAUC for plasma AdV viremia ( $\log_{10}$  copies/mL AdV DNA), as assayed by qPCR, through Day 29 of the Primary Study Period will be summarized by treatment group using descriptive statistics (number of non-missing observations, mean, median, standard deviation, minimum, and maximum). The null hypothesis for this endpoint is that the true mean for posoleucel is greater than or equal to the true mean for placebo, and the alternative hypothesis is that it is less. The null hypothesis will be tested using a one-sided, two-sample t-test with a 0.025 significance level.

The following secondary efficacy endpoints will each be analyzed in the same manner as the primary efficacy endpoint: achieving AdV viremia  $< 400$  copies/mL AdV DNA at Day 29 of the Primary Study Period and AdV disease recurrence during the study among participants who had clearance of AdV viremia (prior to any cross-over).

The Kaplan-Meier estimated median time to resolution of AdV viremia will be presented for each treatment group, together with the 95% confidence interval for the true median. The number and percentage of censored and uncensored participants will be presented by treatment group. The null hypothesis for this endpoint is that the true distributions of time to resolution of AdV viremia are equal for posoleucel and placebo, and the alternative hypothesis is that the true distributions are different, with the time to resolution of AdV viremia being less for posoleucel. The null hypothesis will be tested using a one-sided log-rank test with a 0.025 significance level.

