## **Assessment Overview**

Viral load of AdV will be measured at the central laboratory at each visit from blood and stool samples and at Day -21 to -1 and Day 29 from nasopharyngeal swab. Blood specimens collected should be analyzed by the central laboratory for screening purposes, however, local laboratory results available up to 5 days prior to and/or during screening will be acceptable to determine eligibility. For the inclusion criterion requiring two consecutive and rising AdV viremia results exceeding 1,000 copies/mL, the two consecutive viremia results used to determine eligibility must have been assayed at the same laboratory, preferably the central laboratory however, local lab results are also acceptable (with Medical Monitor approval). This process is expected to expedite the randomization and dosing of participants whose clinical status may rapidly deteriorate. A central laboratory blood sample must be collected prior to dosing on Day 1. All study analyses will continue to be performed using viral load data from the central laboratory.

Participants will be followed weekly for viremia and viral load in the stool while symptomatic. For participants who require intubation and/or undergo bronchoscopy with bronchoalveolar lavage (BAL), a sample of BAL fluid should, when possible, be obtained for AdV viral load determination at the central laboratory. For participants who develop symptoms and/or signs of possible AdV-associated neurological disease, and whose treating physician determines that laboratory evaluation of cerebrospinal fluid (CSF) for diagnostic and/or monitoring reasons is clinically indicated, CSF samples for AdV viral load determination should, when possible, be sent to the central laboratory. In all cases, BAL and CSF samples required for routine clinical care of the patient take precedence over these study-related evaluations.

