**OBJECTIVES AND ENDPOINTS**

Objectives	Endpoints
Primary Efficacy	

 
To compare the percent of participants who have clearance of AdV viremia at Day 29 in participants receiving posoleucel and SoC to that in participants receiving placebo and SoC.
 
	
 
Proportion of participants with undetectable viremia (less than lower limit of quantitation [LLOQ]) at Day 29.
 

Primary Safety	

 
To determine the safety and tolerability of posoleucel by analyzing the incidence and severity of treatment-emergent adverse events (TEAEs), including individual AEs of special interest (AESIs).
 
	
 
Incidence and severity of TEAEs, including individual AESIs, during the study.
 

Key Secondary Efficacy	

 
To determine the percent of participants who develop target organ AdV disease (eg, lower tract respiratory disease documented radiographically, AdV-associated hemorrhagic cystitis, severe hepatitis) or whose target organ disease progresses during the study.
 
	
 
Proportion of participants with disease progression or non-relapse mortality during the study. Progression is defined as: 
 
progression from viremia to target organ disease (for participants without target organ disease at screening), or
 
progression of target organ disease (for participants with target organ disease at screening).
 
 
 

Other Secondary Efficacy	

 
To evaluate the effect of posoleucel on AdV viremia over a 28-day period.
 
	
 
Proportion of participants with undetectable viremia (less than LLOQ) at Day 29 in participants: 
 
without AdV disease at screening.
 
with AdV disease at screening.
 
 
 
Time-averaged area under the concentration-time curve (AAUC) for plasma AdV viremia (<math>\log_{10}</math> copies/mL AdV DNA) as assayed by quantitative polymerase chain reaction (qPCR) through Day 29 for all participants.
 
AAUC for plasma AdV viremia (<math>\log_{10}</math> copies/mL AdV DNA) as assayed by qPCR through Day 29 for participants with no target organ disease at screening.
 

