### **9.1 Efficacy Assessments**

#### **9.1.1 Viral Load Detection Using Quantitative Polymerase Chain Reaction**

Samples will be collected for viral load detection as shown in the SoA ([Section 2](#)) and [Appendix 3](#).

Viral load of AdV in blood, stool, and nasopharyngeal samples will be measured by qPCR, performed by the central laboratory during the study. Blood and stool samples will be stored for potential future virus genotypic or viral load analysis.

During Screening, blood specimens may be collected locally in addition to a central laboratory sample. Local laboratory results available up to 5 days prior to or during screening may be used to initiate screening activities and support eligibility determination. For the inclusion criterion requiring two consecutive and rising AdV viremia results exceeding 1,000 copies/mL, the two consecutive viremia results used to determine eligibility must have been assayed at the same laboratory, preferably the central laboratory. Participants may be randomized and dosed (with Medical Monitor approval) based on local laboratory AdV viremia results. This process is expected to expedite the randomization and dosing of participants whose clinical status may rapidly deteriorate.

All study analyses will continue to be performed using viral load data from the central laboratory.

While not a routine evaluation in this study, any participants who manifest clinical signs and/or symptoms of AdV hemorrhagic cystitis should have a urine sample sent to the central laboratory

for determination of AdV urine viral load. For this subset of participants, AdV urine viral loads should be measured weekly at the central laboratory until resolution of hemorrhagic cystitis.

For participants who require intubation and/or undergo bronchoscopy with bronchoalveolar lavage (BAL), a sample of BAL fluid should, when possible, be obtained for AdV viral load determination at the central laboratory. For participants who develop symptoms and/or signs of possible AdV-associated neurological disease, and whose treating physician determines that laboratory evaluation of cerebrospinal fluid (CSF) for diagnostic and/or monitoring reasons is clinically indicated, CSF samples for AdV viral load determination should, when possible, be sent to the central laboratory. In all cases, BAL and CSF samples required for routine clinical care of the patient take precedence over these study-related evaluations.

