3.1.3 Definition of Baseline

Baseline is defined as the last non-missing measurement prior to the first dose of study treatment. This can be on Day 1 as long as the measurement is taken prior to the first dose.

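### The Protocol compares AAUC with an unadjusted t-test; adjusting for the pre-dose viral load would gain precision and needs no new data

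*Protocol*

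**What the plan says.** Protocol section 4 lists AAUC twice among the other secondary efficacy endpoints: once "through Day 29 for all participants" and once for those without target organ disease at screening. Section 10.3.1.3, repeated in the synopsis, says AAUC is to be "summarized by treatment group using descriptive statistics (number of non-missing observations, mean, median, standard deviation, minimum, and maximum". It then sets a one-sided hypothesis of a lower mean on posoleucel, to be tested with a "one-sided, two-sample t-test with a 0.025 significance level". It names no covariate and no stratum.

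The binary endpoints are treated differently. Section 10.3.1.1 fits a logistic model with "the following covariates: level of viremia at Baseline" (split at 10,000 copies/mL), age (split at 12 years) and absolute lymphocyte count. The key secondary endpoint, the 400 copies/mL endpoint and recurrence follow the same method. SAP section 3.4.2 identifies viremia level and age group as the two randomization strata.

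The baseline value is planned for every dosed participant:
- Synopsis, Assessment Overview: "A central laboratory blood sample must be collected prior to dosing on Day 1".
- Protocol 9.1.1: "All study analyses will continue to be performed using viral load data from the central laboratory".
- SAP 3.1.3: "Baseline is defined as the last non-missing measurement prior to the first dose of study treatment".

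The SAP was written after the trial stopped for futility. It limits efficacy to the primary endpoint (sections 1 and 3.4) and rules out hypothesis tests (section 3.1).

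**The concern.** A load averaged over 28 days starts from the pre-dose level. Two participants with the same decline but different starting levels have different AAUC values, and a two-sample t-test counts that difference as noise. Inclusion criterion 2 sets no upper limit on viral load, and the strata separate participants only at 10,000 copies/mL, so the continuous level can still vary widely within a stratum.

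The choice also sits oddly beside the rest of the Protocol. AAUC is the one quantitative viral-load endpoint with a formal between-arm test of means, yet it gets no baseline adjustment, while endpoints that reduce viral load to yes or no do. Section 5.4 cites overall viral burden as a predictor of mortality in pediatric recipients, so AAUC has some interest of its own.

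At stake are the power of the AAUC test, the width of its confidence interval, and how far a chance difference in baseline load can move the estimate.

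**Working it through.** **Inputs.** 82 dosed participants (Protocol 10.1), 41 per arm (5.2), 1:1 allocation (synopsis), one-sided 0.025 (10.3.1.3). The documents give no SD, effect size or power for AAUC and no baseline-AAUC correlation. Effects are therefore in SD units, and the correlation r is assumed to lie between 0.3 and 0.7.

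**1. The plan's own figure.** For 0.55 versus 0.25, two-sided 0.05 and 80% power, with mean rate 0.40:

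n per arm = [1.960 × √(2 × 0.40 × 0.60) + 0.842 × √(0.55 × 0.45 + 0.25 × 0.75)]² / 0.30² = (1.358 + 0.555)² / 0.09 = 40.7, rounded up to 41.

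The total is 82, which matches; power at 41 per arm is 80.3%. This sizes the primary endpoint only.

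**2. The t-test as planned.** The SE of a mean difference is √(2/41) = 0.221 SD. The difference detectable with 80% power is (1.960 + 0.842) × 0.221 = 0.62 SD. Power at 0.5 SD is Φ(0.5/0.221 − 1.960) = Φ(0.304), about 62%.

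**3. Adjusted for baseline.** ANCOVA multiplies the residual SD by √(1 − r²). The unadjusted trial of equal precision has 82/(1 − r²) participants.

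| Assumed r | Residual SD | Detectable at 80% power | Power at 0.5 SD | Equivalent N |
|---|---|---|---|---|
| 0 (t-test) | 1.000 | 0.62 SD | 62% | 82 |
| 0.3 | 0.954 | 0.59 SD | 66% | 90 |
| 0.5 | 0.866 | 0.54 SD | 74% | 109 |
| 0.7 | 0.714 | 0.44 SD | 89% | 161 |

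**4. Simulation check** (8,000 runs per setting, 41 per arm, simple randomization). Under no effect, the t-test rejected in 0.024 to 0.028 of runs and ANCOVA in 0.025 to 0.026, so both hold the 0.025 level to within simulation error. At 0.5 SD the t-test had about 61% power, against 65%, 73% and 88% for ANCOVA at r = 0.3, 0.5 and 0.7. With r = 0 the two were nearly equal (62.3% and 61.8%), so adjusting for a useless baseline costs almost nothing.

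**5. Chance imbalance.** Under simple randomization the baseline difference between arms has an SE of √(2/41) = 0.22 SD. If only 20 per arm were analysed (an assumption; the final number is not stated), it would be √(2/20) = 0.32 SD. Stratifying at 10,000 copies/mL removes part of this but does not balance the continuous level.

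**6. Is the range of r reasonable?** A rough trajectory model assumed a baseline SD of 0.8 to 1.2 log10, a weekly-slope SD of 0.3 to 0.8 log10 and a floor at the 32 copies/mL LLOQ. It gave correlations of 0.45 to 0.86. This shows that 0.5 to 0.7 is plausible, but it is not evidence from the trial.

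**The case against.** The strongest reply is that nothing here is wrong. A two-sample t-test is valid in a randomized trial, and its standard error already allows for chance baseline differences. The log-rank test for time to resolution is also unadjusted, so the Protocol uses simple tests for its non-binary secondary endpoints. AAUC is outside the sequence that controls type I error, which names the primary and key secondary endpoints. No power is claimed for AAUC, and the SAP no longer analyses it. All of this stands, and it limits the point to efficiency.

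A reader might infer more, but the documents do not support these readings:
- *Baseline is the strongest driver of AAUC, or AAUC is the most informative virologic secondary endpoint.* No text ranks either. There is no AAUC formula and no statement on whether AAUC is baseline-corrected, and the correlation depends on that.
- *The gain is large.* That needs a high r. At r = 0.3 it is about four percentage points of power.
- *The t-test is biased or anticonservative.* The simulation shows neither under randomization.
- *Baseline loads start at 1,000 copies/mL.* That is a screening threshold for one entry route. The Amendment 3 rationale describes some participants clearing viremia between randomization and treatment.
- *Reported results are affected, or any later report must use this test.* The SAP excludes AAUC, and Protocol 10.3 calls itself a summary that leaves detail to the SAP.

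**Conclusion.** The point holds as an efficiency remark on the Protocol's planned AAUC analysis and on any AAUC report made under it. At the planned 41 per arm and a 0.5 SD difference, the unadjusted test gives up about 4, 12 or 27 percentage points of power (62% against 66%, 74% or 89%) at r = 0.3, 0.5 or 0.7. The size rests on the assumed r, on a roughly linear relation between baseline and AAUC, and on the planned rather than the achieved sample size. The direction is secure if baseline load predicts AAUC at all. It is an optional improvement and changes nothing that the SAP reports.

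**What to change.** If AAUC is reported, replace the t-test with an ANCOVA of AAUC on treatment, continuous baseline log10 AdV DNA from the central laboratory (baseline as in SAP 3.1.3) and the age stratum. Baseline absolute lymphocyte count may be added to match the primary model. The viremia stratum adds little once the continuous value is in. Test treatment one-sided at 0.025 and report the adjusted difference with its 95% confidence interval.

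The change of test costs one sentence and no new data. With baseline as a covariate, the treatment estimate is the same for raw AAUC and for AAUC minus baseline, which removes one ambiguity. The AAUC formula and the handling of values below the LLOQ, deaths and cross-over before Day 29 need a few lines under either test. Write the model down before AAUC is computed by arm; otherwise label the analysis post hoc.
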